Appendix 3 Criteria for Identifying ECG Measurements of Potential Clinical Relevance

[figure not shown]
Variable	Criterion Value a	Change Relative to Baseline a
Rhythm		
Sinus tachycardia b	≥ 110 bpm	increase of $\geq 15$ bpm
Sinus bradycardia c	$\leq$ 60 bpm	decrease of $\geq 15$ bpm
Supraventricular premature beat	all	not present → present
Ventricular premature beat	all	not present → present
Supraventricular tachycardia	all	not present → present
Ventricular tachycardia	all	not present → present
Atrial fibrillation	all	not present → present
Atrial flutter	all	not present → present
Conduction		
1° atrioventricular block	$PR \ge 200 \text{ msec}$	increase of $\geq$ 50 msec
2° atrioventricular block	all	not present → present
3° atrioventricular block	all	not present → present
Left bundle-branch block	all	not present → present
Right bundle-branch block	all	not present → present
Pre-excitation syndrome	all	not present → present
Other intraventricular conduction block d	QRS $\geq$ 120 msec	increase of $\geq 20$ msec
Infarction		
Acute or subacute	all	not present $\rightarrow$ present
Old	all	not present → present ≥ 12 weeks post-trial entry
ST/T Morphological		_ 12 weeks post that only
Myocardial Ischemia	all	not present → present
Symmetrical T-wave inversion	all	not present → present
Increase in QTc	QTcF $\geq$ 450 msec for males, $\geq$ 470 msec for females	increase of 60 msec from baseline

<sup>a The criterion value and change relative to baseline represented in this table are intended to identify ontreatment values outside of normal changes and that could potentially be clinically relevant. In order to be identified as potentially clinically relevant, the on-treatment value must meet the "Criterion Value" and also represent a change from the subject's baseline value of at least the magnitude shown in the "Change Relative to Baseline" column. When evaluating these values the emotional state of the subject must be taken into consideration (eg, crying, screaming) and documented as applicable.

<sup>bNo current diagnosis of supraventricular tachycardia, ventricular tachycardia, atrial fibrillation, atrial flutter, or other rhythm abnormality.

<sup>cNo current diagnosis of atrial fibrillation, atrial flutter, or other rhythm abnormality.

<sup>dNo current diagnosis of left bundle branch block or right bundle branch block.

#### **ADDITIONAL RISK TO THE SUBJECT:**

There is no additional risk to the subjects.

#### **Trial Conduct for COVID-19**

All procedures and assessments in the protocol are to be followed to the fullest extent possible. The sponsor, in coordination with the sites, investigators, and medical monitor, will continuously monitor and evaluate the benefits and risks to subject participation in the clinical trial as it relates to COVID-19. If any protocol-specified activities were not able to be performed, or cannot be performed due to COVID-19 considerations, the appropriate measures to be followed will be provided in this document.

## **List of Abbreviations and Definitions of Terms**

Definition
Aberrant Behavior checklist
Adrenocorticotropic hormone
Attention-deficit/hyperactivity disorder
Adverse event
Abnormal Involuntary Movement Scale
Barnes Akathisia Rating Scale
Blood pressure
Clinical Global Impression - Severity
Creatine phosphokinase
Clinical research organization
Columbia-Suicide Severity Rating Scale
Cytochrome P450
Electrocardiogram
Electronic case report form
End of treatment
Extrapyramidal symptoms
Early termination
Females of child bearing potential
Glycosylated hemoglobin
Investigational medicinal product
QT interval corrected for heart rate by Bazett's formula
QT interval corrected for heart rate by Fridericia's formula
Serious adverse event
Simpson Angus Scale
Thyroid-stimulating hormone

## 1 Trial 331-201-00191 COVID-19 Protocol Summary

#### 1.1 Trial Design Schematic

[figure not shown]

Figure 1.1-1 COVID-19 Impact Trial Design Schematic - Subjects Who Rollover Directly From Trial 331-201-00148

Note: In order to be eligible for this trial, the baseline visit must be in office per the protocol. Eligible subjects are those subjects who complete Trial 331-201-00148. Subjects who were not able to rollover directly into this trial (Trial 331-201-00191) or are terminated early from Trial 331-201-00148 due to the COVID-19 pandemic will have an opportunity to enter this trial upon completion of in office screening and baseline visits as detailed in Figure 1.1-2.

[figure not shown]

Figure 1.1-2 Trial Design Schematic - Delayed Rollover Subjects From Trial 331-201-00148

Note: In order to eligible for this trial, the screening and baseline visits must be in office.

#### 1.2 Schedules of Assessments

	Screening/ Baseline						at Period			ЕОТ	Follow- up	
Assessment	Last visit from Trial 331-201- 00148/ Baseline for Trial 331-201- 00191	Week 1 (Day 7 ± 2 days)	Week 2 (Day 14 ± 2 days)	Week 3 (Day 21 ± 2 days)	Week 4 (Day 28 ± 2 days)	Week 8 (Day 56 ± 2 days)	Week 14 (Day 98 ± 2 days)	Week	Week	Week 26/ ET (Day 182 ± 2 days)  In office	21 (± 2) days after last dose of IMP	Notes
Informed	X	, 11 (414)	, 11 ttal	, 11 002001	, 11 ttan1	, 11 00001	, 11 tutti	, 11 00001	7 11 00001		•	
consent/assent, update medical history, as needed												
Prior medications	X											
Inclusion/exclusion criteria	X											
CGI-S	X	X	X	X	X	X	X	X	X	X		
SAS, AIMS, & BARS	X		X (AIMS and BARS)				X (AIMS and BARS)			X		Section 4.1.3
C-SSRS	X	X	X	X	X	X	X	X	X	X		
ABC	X	X	X	X	X	X	X	X	X	X		
CCI CCI												
Physical	X									X		
examination				L		]						

Table 1.2-1	COVII	D-19 Imp	act Sche	dule of A	ssessmen	ts - Subj	ects Who	Rollove	r Directl	y From		1-201-00148		
	Screening/ Baseline		26-week Open-label Treatment Period							EOT	Follow- up			
Assessment	Assessment	Last visit from Trial 331-201- 00148/ Baseline for Trial 331-201- 00191	from Trial 331-201- 00148/ Baseline for Trial 331-201-	Week 1 (Day 7 ± 2 days)	Week 2 (Day 14 ± 2 days)	Week 3 (Day 21 ± 2 days)	Week 4 (Day 28 ± 2 days)	Week 8 (Day 56 ± 2 days)	Week 14 (Day 98 ± 2 days)	Week 18 (Day 126 ± 2 days)	Week 22 (Day 154 ± 2 days)	Week 26/ ET (Day 182 ± 2 days)	21 (± 2) days after last dose of IMP	Notes
	In office a	Virtual	Virtual	Virtual	Virtual	Virtual	Virtual	Virtual	Virtual	In office	By Tele- phone			
Body weight and waist circumference	X						X			X		Section 4.1.1		
Height	X						X			X				
Vital signs	X	X	X	X	X	X	X	X	X	X				
ECG	X									X				
Clinical laboratory tests (hematology, serum chemistry, and urinalysis)	X									X				
HbA1c	X									X				
Prolactin	X									X				
Urine pregnancy test	X						X			X		Section 4.1.2		
ACTH	X									X				
Cortisol	X									X				
TSH with reflex to free T4 if abnormal	X									X				
Coagulation parameters	X									X				

Table 1.2-1	Table 1.2-1         COVID-19 Impact Schedule of Assessments - Subjects Who Rollover Directly From Trial 331-201-00148											
	Screening/ Baseline 26-week Open-label Treatment Period										Follow- up	
Assessment	Last visit from Trial 331-201- 00148/ Baseline for Trial 331-201- 00191	Week 1 (Day 7 ± 2 days)	Week 2 (Day 14 ± 2 days)	Week 3 (Day 21 ± 2 days)	Week 4 (Day 28 ± 2 days)	Week 8 (Day 56 ± 2 days)	Week 14 (Day 98 ± 2 days)	Week 18 (Day 126 ± 2 days)	Week 22 (Day 154 ± 2 days)	Week 26/ ET (Day 182 ± 2 days)	21 (± 2) days after last dose of IMP	Notes
	In office a	Virtual	Virtual	Virtual	Virtual	Virtual	Virtual	Virtual	Virtual	In office	By Tele- phone	
Adverse events	X	X	X	X	X	X	X	X	X	X	X	
Concomitant medications	X	X	X	X	X	X	X	X	X	X	X	
Dispense IMP	X	X	X	X	X	X	X	X	X			
IMP accountability	X	X	X	X	X	X	X	X	X	X		

ABC = Aberrant Behavior Checklist; ACTH = Adrenocorticotropic hormone; AIMS = Abnormal Involuntary Movement Scale; BARS = Barnes Akathisia Rating Scale; BP = blood pressure; CGI-S = Clinical Global Impression - Severity of Illness scale; C-SSRS = Columbia-Suicide Severity Rating Scale; ECG = electrocardiogram; EOT = end of treatment; ET = early termination; HbA1c = glycosylated hemoglobin; IMP = investigational medicinal product; SAS = Simpson-Angus Scale; TSH = thyroid-stimulating hormone.

Note: If efficacy or safety assessments cannot be obtained at consecutive virtual visits, the investigator should discuss possible discontinuation of the subject with the medical monitor.

<sup>aIn order to eligible for this trial, the baseline visit must be in office per the protocol. Eligible subjects are those subjects who complete Trial 331-201-00148. Subjects who were not able to rollover directly into this trial (Trial 331-201-00191) or are terminated early from Trial 331-201-00148 due to the COVID-19 pandemic will have an opportunity to enter this trial upon completion of in office screening and baseline visits as detailed in Table 1.2-2.

Table 1.2-2		ID-19 In	pact Sc				Delayed		er Subje	ects Fro	m Tria	1 331-201	-00148									
	Screening (Day -28				ЕОТ	Follow- up																
Assessment	to -1)	to -1)	to -1)	to -1)	to -1)	to -1)	to -1)	to -1)	to -1)	to -1)	Base line (Day 1)	Week 1 (Day 7 ± 2 days)	Week 2 (Day 14 ± 2 days)	Week 3 (Day 21 ± 2 days)	Week 4 (Day 28 ± 2 days)	Week 8 (Day 56 ± 2 days)	Week 14 (Day 98 ± 2 days)	Week 18 (Day 126 ± 2 days)	Week 22 (Day 154 ± 2 days)	Week 26/ ET (Day 182 ± 2 days)	21 (± 2) days after last dose of IMP	Notes
	In office a	In office	Virtual	Virtual	Virtual	Virtual	Virtual	Virtual	Virtual	Virtual	In office	By Tele- phone										
Informed	X																					
consent/assent																						
Inclusion/exclusion	X	X																				
criteria																						
Medical history	X																					
Psychiatric history	X																					
Verification of stability of comorbid conditions b	X																					
Prior medications and washout, if applicable	X																					
CGI-S	X	X	X	X	X	X	X	X	X	X	X											
SAS, AIMS, & BARS		X		X (AIMS and BARS)				X (AIMS and BARS)			X											
C-SSRS	X	X	X	X	X	X	X	X	X	X	X											
ABC	X	X	X	X	X	X	X	X	X	X	X											
CCI				l								]										

	Screening (Day -28	Screening   26-week Open-label Treatment Period   (Day -28									EOT	Follow- up	
Assessment	to -1)  In office a	Base line (Day 1)	Week 1 (Day 7 ± 2 days)	1 2 (Day 7 ± 2 days) 4 ± 2 days)	3 (Day 2 21 ± 2 s) days)	Week	days)	3 14 ay (Day ± 2 98 ± 2 ys) days)	Week	Week   22   (Day   154 ± 2   days)	Week 26/ ET (Day 182 ± 2 days)	21 (± 2) days after last dose of IMP	Notes
		In office	Virtual								In office		
CCI													
Physical examination	X										X		
Body weight and waist circumference	X	X						X			X		
Height	X							X			X		
Vital signs	X	X	X	X	X	X	X	X	X	X	X		
ECG	X c	X d									X		
Clinical laboratory tests (hematology, serum chemistry, and urinalysis)	X c	X d									X		
HbA1c	X										X		
Prolactin	X										X		
Urine drug screen	X												
Blood alcohol test	X												
Urine pregnancy test	X							X			X		
ACTH	X										X		
Cortisol	X										X		

	Screening (Day -28	26-week Open-label Treatment Period										Follow- up	
Assessment	to -1)	Base line (Day 1)	Week 1 (Day 7 ± 2 days)	Week 2 (Day 14 ± 2 days)	Week 3 (Day 21 ± 2 days)	Week 4 (Day 28 ± 2 days)	Week 8 (Day 56 ± 2 days)	Week 14 (Day 98 ± 2 days)	Week 18 (Day 126 ± 2 days)	Week 22 (Day 154 ± 2 days)	Week 26/ ET (Day 182 ± 2 days)	21 (± 2) days after last dose of IMP	Notes
	office a	office	Virtual	Virtual	Virtual	Virtual	Virtual	Virtual	Virtual	Virtual	office	phone	
TSH with reflex to	X										X		
free T 4 if abnormal													
Coagulation parameters	X										X		
Adverse events	X	X	X	X	X	X	X	X	X	X	X	X	
Concomitant medications	X	X	X	X	X	X	X	X	X	X	X	X	
Dispense IMP		X	X	X	X	X	X	X	X	X			
IMP accountability			X	X	X	X	X	X	X	X	X		

Note: If efficacy or safety assessments cannot be obtained at consecutive virtual visits, the investigator should discuss possible discontinuation of the subject with the medical monitor.

In order to eligible for this trial, the screening and baseline visits must be in office. All other visits of the open-label treatment period after the baseline visit can be virtual or performed per the protocol.

<sup>aDelayed rollover subjects must agree to discontinue all prohibited medications during the screening period as summarized in Table 6-1.

<sup>bThe investigator should verify the stability of comorbid conditions and that there is no potential new diagnosis since the screening vist in Trial 331-201-00148.

<sup>cThe screening period may be extended in order to repeat clinical laboratory tests and ECGs; if an extension is required, the site should contact the medical monitor.

<sup>dBaseline clinical laboratory tests (hematology, serum chemistry, and urinalysis) and ECGs are not collected if screening clinical laboratory tests/ECGs were obtained within 28 days prior to the baseline visit and within normal ranges.

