Propoxyphene	Coagulation Parameters:		
	PT		
	aPTT		
	INR		

aPTT = activated partial thromboplastin time; ALT = alanine aminotransferase; AST = aspartate aminotransferase; BUN = blood urea nitrogen; CPK = creatine phosphokinase; INR = international normalized ratio; GGT = gamma glutamyl transferase; HbA1c = glycosylated hemoglobin; HDL = high density lipoprotein; LDH = lactic dehydrogenase; LDL = low density lipoprotein, MCH = mean corpuscular hemoglobin; PT = prothrombin time; RBC = red blood cell; RDW = red cell distribution width; WBC = white blood cell.

The total volume of blood to be collected during the trial will be documented in the ICF/IAF.

A urine pregnancy test will be conducted in all females of child-bearing potential (FOCBP) prior to trial intervention; results must be available prior to the administration of the IMP. A confirmatory serum pregnancy test will be done for subjects with a positive urine test. Subjects with a positive pregnancy test result at screening will be excluded from the trial. The frequency of pregnancy tests may be modified based on local regulatory requirements and pregnancy tests can be performed at any point during trial if pregnancy is suspected.

Any value outside the normal range will be flagged for the attention of the investigator, who must indicate whether or not a flagged value is of clinical significance. If 1 or more values are questionable, the test(s) may be repeated. If the result of any test (or repeat test, if done) is indicated as clinically significant in the samples taken during the screening period, the subject will NOT be enrolled into the trial without the permission of the medical monitor. In addition, follow-up unscheduled laboratory tests should be performed on clinically significant abnormalities. Unscheduled laboratory tests may be repeated at any time at the discretion of the investigator for appropriate medical care.

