#### 5.5 Pregnancy

Females of child-bearing potential (FOCBP) are defined as female subjects for whom menstruation has started and who are not documented as sterile (ie, have had a bilateral oophorectomy and/or hysterectomy or who have been postmenopausal for at least 12 months).

For FOCBP and for men who are sexually active, there must be a documented agreement that the subject and/or their partner will take effective measures (ie, double-barrier method) to prevent pregnancy during the course of the trial and for 30 days after the last

dose of IMP. If employing birth control, 2 of the following precautions must be used: vaginal diaphragm, intrauterine device, birth control pill, birth control implant, birth control depot injection, condom with spermicide, or sponge with spermicide. The contraceptive methods will be documented at each trial visit.

Before enrolling FOCBP in this clinical trial, investigators must review the below guidelines about trial participation with all FOCBP. The topics should generally include:

- General information
- Informed consent/assent form
- Pregnancy prevention information
- Drug interactions with hormonal contraceptives
- Contraceptives in current use
- Guidelines for the follow-up of a reported pregnancy

Before trial enrollment, FOCBP must be advised of the importance of avoiding pregnancy during trial participation and the potential risk factors for an unintentional pregnancy. The subject and the subject's legally acceptable representative (eg, guardian) must sign an ICF/IAF stating that the above-mentioned risk factors and the consequences were discussed with them.

A urine pregnancy test for human chorionic gonadotropin will be performed at screening on all FOCBP and female subjects  $\geq 12$  years of age and all female subjects  $\leq 12$  years of age, if menstruation has started. If a urine test is performed and is positive, the investigator will follow up with a confirmatory serum test.

During the trial, all FOCBP should be instructed to contact the investigator immediately if they suspect they might be pregnant (eg, missed or late menstrual cycle).

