If a subject is suspected to be pregnant before she receives IMP, the IMP administration must be withheld until the results of serum pregnancy tests are available. If the pregnancy is confirmed, the subject must not receive the IMP and must not be enrolled in the trial. If pregnancy is suspected while the subject is taking IMP, the IMP must be withheld immediately (if reasonable, taking into consideration any potential withdrawal risks) until the result of the pregnancy test is known. If pregnancy is confirmed, the IMP will be permanently discontinued in an appropriate manner (eg, dose tapering if necessary for subject safety) and the subject will be withdrawn from the trial. Exceptions to trial discontinuation may be considered for life-threatening conditions only after consultations

with the Clinical Safety and Pharmacovigilance department (see the cover page of this protocol for contact information).

The investigator must immediately notify the sponsor of any pregnancy associated with IMP exposure during the trial and for 30 days after the last dose of IMP, and record the event on the IRE form and forward it to the sponsor. The sponsor will forward Pregnancy Surveillance Form(s) for monitoring the outcome of the pregnancy.

Protocol-required procedures for trial discontinuation and follow-up must be performed on the subject unless contraindicated by pregnancy (eg, x-ray studies). Other appropriate pregnancy follow-up procedures should be considered, if indicated. In addition, the investigator must report to the sponsor, on appropriate Pregnancy Surveillance Form(s), follow-up information regarding the course of the pregnancy, including perinatal and neonatal outcome. Infants will be followed for a minimum of 6 months from the date of birth.

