#### 4.1.2 Pregnancy

Pregnancy tests will be performed as described in the protocol at the virtual visits defined in this COVID-19 Addendum Schedules of Assessments (Table 1.2-1 and Table 1.2-2) with the following changes:

- For planned visits that require a pregnancy test for females of childbearing potential (FOCBP), the site will provide the necessary tests and instructions so the test may be performed at home;
- Applicable subjects will perform a pregnancy test prior to dosing with IMP, ensuring a date and time-stamped picture or video of the result is taken. The caregiver is to provide/show the result during the virtual visit.
  - If negative, site to inform the subject to proceed with dosing.
  - If positive, the site must instruct the subject to immediately stop taking IMP, and the site will refer to the Pregnancy section of the protocol for appropriate immediately reportable event reporting.

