# 6 Prohibited Medications (Delayed Rollover Subjects From Trial 331-201-00148)

Delayed rollover subjects must agree to discontinue all prohibited medications during the screening period, after signing the informed consent form/informed assent form, in order to meet the protocol-specified washout periods. Table 6-1 provides the required duration of washout for selected prohibited medications. All other prohibited medications must be discontinued at least 24 hours before the first dose of IMP.

Table 6-1 List of Washout of Prohibited Medications for Delayed Rollover Subjects From Trial 331-201-00148							
Medication	Required Washout Prior to Dosing						
Antipsychotics Oral aripiprazole Oral antipsychotics (other than cariprazine and clozapine) Depot or long-acting injectable antipsychotics or clozapine	14 days 7 days EXCLUDED						
Antidepressants Fluoxetine or Symbyax Monoamine oxidase inhibitors Citalopram and escitalopram Venlafaxine and desvenlafaxine All other antidepressants	28 days 14 days 14 days 14 days 14 days						
Other psychotropics Atomoxetine	For subjects without ADHD diagnosis - 7 days						
Stimulants	Minimum 5× half- life for subjects without diagnosis of ADHD						
Mood stabilizers (ie, lithium or anticonvulsants)  Varenicline	7 days 5 days						
Oral benzodiazepines used as rescue therapy during washout a Lorazepam, oxazepam, diazepam, or clonazepam Other benzodiazepines CYP2D6 inhibitors and CYP3A4 inhibitors and inducers (see Table 4.1-3 of the protocol).	8 hours before scales b 14 days 14 days						

ADHD = attention-deficit/hyperactivity disorder; CYP = cytochrome P450.

<sup>aUse of intramuscular benzodiazepines and continual use of oral benzodiazepines are prohibited throughout the trial. However, limited use of specific oral benzodiazepines is permitted during screening to treat agitation or insomnia as shown in Table 4.1-2 of the protocol.

<sup>bBenzodiazepines must not be administered within 8 hours prior to scheduled efficacy assessments, and EPS scales. Investigators are encouraged to delay scale administration until 8 hours have elapsed, if at all possible. However, if delaying administration of efficacy and EPS scales is not feasible, the scales should still be administered and the use of benzodiazepine documented, including a notation of the drug name, dose, and time of administration in eSource.

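### Delayed rollovers have no scheduled pregnancy test at the Day 1 baseline, so the first dose can rest on a negative result 28 or more days old

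*Protocol*

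**What the plan says.** In the COVID-19 Addendum, section 1.2, Table 1.2-2 covers subjects who could not roll over directly. Its row "Urine pregnancy test" is marked at Screening (Day -28 to -1), Week 14 and Week 26/ET. The Baseline (Day 1) cell is empty, although IMP is dispensed at that visit and it must be held in the office.

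Two footnotes bear on timing. Footnote c: "The screening period may be extended in order to repeat clinical laboratory tests and ECGs; if an extension is required, the site should contact" (here, the medical monitor). It states no maximum length. Footnote d lists hematology, serum chemistry, urinalysis and ECGs as baseline tests that "are not collected if screening clinical laboratory tests/ECGs were obtained within 28 days prior to the baseline visit and within normal ranges". It is not attached to the pregnancy row.

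The main protocol fixes the test by visit, not by age of result. Section 3.7.3.2: "A urine pregnancy test will be conducted in all females of child-bearing potential (FOCBP) prior to trial intervention; results must be available" before IMP is given. Section 5.5: "A urine pregnancy test for human chorionic gonadotropin will be performed at screening on all FOCBP". Neither section says how old the result may be at first dose.

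Addendum section 4.1.2 does not fill the gap, because it concerns tests done remotely: "Pregnancy tests will be performed as described in the protocol at the virtual visits defined in this COVID-19 Addendum Schedules of Assessments". In Table 1.2-2 the only virtual visit with a pregnancy test is Week 14.

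**The concern.** In the main protocol, screening and baseline are one visit (section 3.7.1.1) and dosing starts the next day. A test placed at screening is then effectively a test at first dose. The Addendum separates the two visits by up to four weeks for delayed rollovers but leaves the test at the earlier one.

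The separation can be deliberate and long. Addendum section 6 places washout inside it: "Delayed rollover subjects must agree to discontinue all prohibited medications during the screening period, after signing the informed consent form/informed assent form". A pregnancy may begin in that period, or may have been too early to detect when it started.

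The protocol does not allow dosing in confirmed pregnancy, and Addendum Table 3.2-1 excludes a subject with a positive test before IMP. Eligibility is checked again on Day 1, but the site then has no new scheduled result for that criterion. What is at stake is fetal exposure to IMP that a simple test could prevent. No estimate or summary table is affected.

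**Working it through.** The plan states no figure for this interval, so there is none to reproduce. The check reads the table by cell and then applies day arithmetic.

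**Row reading, Table 1.2-2 (columns in order: Screening, Baseline, Weeks 1, 2, 3, 4, 8, 14, 18, 22, 26/ET, Follow-up).**

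| Row | Marked at |
|---|---|
| Urine pregnancy test | Screening, Week 14, Week 26/ET |
| Body weight and waist circumference | Screening, Baseline, Week 14, Week 26/ET |
| Laboratory tests | Screening, Baseline (conditional, footnote d), Week 26/ET |

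**Age of the result at first dose.** SAP section 10.2 makes Day 1 the first day of dosing and has no Day 0, so Day -k lies k days before Day 1.

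- Screened on Day -1: 1 day.
- Screened on Day -28: 28 days.
- Screening extended by e days: 28 + e days at most. The documents give no limit for e. Assumed values of 7, 14 and 28 days give 35, 42 and 56 days.
- Direct rollovers: tested at the baseline visit, dosed the next day, so 1 day.
- Largest excess over direct rollovers with unextended screening: 28 - 1 = 27 days, plus any extension.

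**Minimum age for subjects who need washout.** Washout starts after consent. Consent and the urine test share the screening column. Assuming that they fall on the same visit, the washouts in Addendum Table 6-1 give these minimum ages:

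| Drug stopped | Minimum age of result |
|---|---|
| Oral antipsychotics other than aripiprazole (cariprazine and clozapine apart); mood stabilizers | 7 days |
| Oral aripiprazole; most antidepressants; CYP2D6 inhibitors, CYP3A4 inhibitors and inducers | 14 days |
| Fluoxetine or Symbyax | 28 days |

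**Does another provision supply a Day 1 test?** Footnote d does not name the pregnancy test. Addendum 4.1.2 is limited to virtual visits. Section 5.5 acts only on suspicion: "If a subject is suspected to be pregnant before she receives IMP, the IMP administration must be withheld until the results of serum pregnancy tests" have come back. None is a routine test at baseline.

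**After the change.** A test read at the Day 1 visit is 0 days old if dosing starts that day, and 1 day old if it starts the next day.

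**The case against.** The strongest reply is that the schedule complies with the protocol: a test is done at screening and its result is known before IMP. That is correct, and this point is a suggested improvement, not a contradiction.

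Footnote d also gives less support than it may seem to. It accepts a normal laboratory or ECG result up to 28 days old, and a Day -28 result is exactly 28 days old on Day 1. Within the standard window a negative pregnancy test is therefore treated like a normal laboratory result, and the missing age limit matters only after an extension. An extension is for repeating laboratory tests or ECGs and involves the medical monitor. This stands. The case for a routine Day 1 test rests mainly on the comparison with direct rollovers and on the fact that pregnancy can begin during screening.

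Day 1 is not unguarded. Subjects agree to two contraceptive methods or abstinence, methods are documented at each visit, a missed or late cycle is to be reported, and eligibility is re-checked. These measures lower the risk, but without a new test none of them reveals a pregnancy that nobody suspects.

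The trial also accepts 98 - 1 = 97 days between Day 1 and the Week 14 test, and 182 - 98 = 84 days from there to Week 26. Those intervals apply to all subjects and are not in question here. Tolerating them on treatment is no reason to omit a check before exposure begins.

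Finally, the washout minimums fall away if a site does the urine test later in the screening window. That is so, and they are given only under the stated assumption.

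**Conclusion.** The point holds. For delayed rollovers, the plan allows a first dose on a negative pregnancy result 1 to 28 days old, or older after an extension, where direct rollovers have a result 1 day old. The 28-day figure is the upper end of the standard window, not the typical case.

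The number of subjects is limited. The SAP (section 4) gives 119 randomized in the parent trial as the ceiling for the whole extension. Only females of child-bearing potential among the delayed rollovers are concerned, and the documents do not say how many there are. The change is worth making because it protects the individual subject at very little cost, not because many are likely to be affected. A Day 1 test narrows the window but does not close it, since a very early pregnancy can still be missed.

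**What to change.** In Table 1.2-2, mark the urine pregnancy test in the Baseline (Day 1) column for females of child-bearing potential, and require that a negative result be read before IMP is released. Keep the screening test. A positive result goes to the serum confirmation that the protocol already provides.

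The cost is one mark in the table and one urine dipstick per subject concerned. No visit is added: the baseline visit is already in the office, and eligibility, vital signs and the C-SSRS are already repeated there. No analysis changes.
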